## Version History

This Statistical Analysis Plan (SAP) for study NN8640-4469 is based on the protocol version 3.0 dated 21 December 2022.

| SAP Version | Date         | Change         | Rationale        |
|-------------|--------------|----------------|------------------|
| 1.0         | 24 June 2024 | Not Applicable | Original version |

## List of abbreviations

|            |   |
|------------|---|
| AE         | adverse event   |
| BMI        | body mass index   |
| DPS        | data points set   |
| FAS        | full analysis set                                       |
| PPFV       | first patient first visit                               |
| GH         | growth hormone  |
| GH-INJ-CTB | Growth Hormone Injection - Child Treatment Burden       |
| GH-PPQ     | Growth Hormone Patient Preference Questionnaire         |
| HV         | height velocity   |
| IGF-1      | insulin-like growth factor 1                            |
| IGFBP-3    | insulin-like growth factor binding protein-3            |
| IMP        | investigational medical product                         |
| ISS        | idiopathic short stature                                |
| IVSed      | end-diastolic interventricular septum thickness         |
| LVIDed     | end-diastolic left ventricular internal diameter        |
| LVIDes     | end-systolic left ventricular internal diameter         |
| LVPWed     | end-diastolic left ventricular posterior wall thickness |
| MAP        | modelling analysis plan                                 |
| MedDRA     | medical dictionary for regulatory activities            |
| MPH        | midparental target height                               |
| NAH        | near adult height                                       |
| NS         | Noonan syndrome   |
| PAS        | participant analysis set                                |
| PD         | pharmacodynamic   |
| PK         | pharmacokinetic   |

SAP Statistical Analysis Plan

SAS safety analysis set

SDS standard deviation score

SGA small for gestational age

TS Turner syndrome

# 1 Introduction

Primary analysis of the primary endpoint addressing the primary estimand was defined in protocol before first patient first visit (FPFV). There are no changes to the analysis described in the protocol.

This SAP is based on the protocol: *A study evaluating the safety and efficacy of once-weekly dosing of somapacitan in a basket study design in paediatric participants with short stature either born small for gestational age or with Turner syndrome, Noonan syndrome or idiopathic short stature*. REAL 9, version 3.0 (dated 21 December 2022). This SAP covers specification of statistical considerations and analyses for efficacy and safety data. SAP 1.0 was created post FPFV.

## 1.1 Objectives, Endpoints, and Estimands

**Table 1 Objectives and endpoints**

| Objectives  | Endpoints  |                                    |               |
|---|--|------------------------------------|---------------|
| Primary   | Title  | Time frame                         | Unit          |
| • To evaluate the safety of once-weekly somapacitan in children, either naïve or non-naïve to GH treatment, within each of the four indications: SGA, TS, NS or ISS.                        | Primary endpoint:
Number of adverse events (AEs)
From baseline (week 0) to week 26   |                                    |               |
| Secondary   | Title  | Time frame                         | Unit          |
| • To evaluate the long-term safety of once-weekly somapacitan in children, either naïve or non-naïve to GH treatment, within each of the four indications: SGA, TS, NS or ISS.              | Secondary supportive safety endpoint:
Number of adverse events (AEs) possibly or probably related to somapacitan
From baseline (week 0) to week 26               |                                    |               |
|   | Number of adverse events (AEs)   | From baseline (week 0) to week 156 | Number of AEs |
| • To evaluate the efficacy of once-weekly somapacitan for in children, either naïve or non-naïve to GH treatment, within each of the four indications: SGA, TS, NS or ISS.                  | Secondary supportive efficacy endpoints:
Height Velocity
From baseline (week 0) to week 26   |                                    |               |
|   | Change in Height SDS   | From baseline (week 0) to week 26  | Score*        |
|   | Change in Height Velocity SDS  | From baseline (week 0) to week 26  | Score*        |
|   | Change in IGF-1 SDS  | From baseline (week 0) to week 26  | Score*        |
|   | Change in IGFBP-3 SDS  | From baseline (week 0) to week 26  | Score*        |
| • To evaluate the steady state pharmacokinetics of once-weekly somapacitan in children, either naïve or non-naïve to GH treatment, within each of the four indications: SGA, TS, NS or ISS. | Secondary supportive efficacy endpoint:
Weekly average somapacitan concentration ( $C_{avg}$ ) based on population PK analysis
From baseline (week 0) to week 26 |                                    |               |
|   |  |                                    | ng/ml         |

\*Positive score indicates that the value is closer to or above the reference population compared to baseline.

## Primary estimand

The primary clinical question of interest is: What is the incidence of AEs from baseline to week 26 in the four populations (SGA, TS, NS or ISS) in all patients while on treatment regardless of dose reduction?

For the primary objective, the same primary estimand is defined for each of the four populations (SGA, TS, NS or ISS) with 5 attributes:

- The treatment condition of interest is defined as somapacitan regardless of dose reduction
- The population targeted by the clinical question: The treatment effect will be assessed separately for each of the four populations (SGA, TS, NS or ISS)
- Endpoint: Number of adverse events from baseline to 26 weeks
- Remaining intercurrent events:
  - Treatment discontinuation for any reason: Participants data will be included up to 14 days after treatment discontinuation. Data collected 14 days after the intercurrent event will be regarded as not relevant for estimation of the treatment effect
  - Dose reduction due to IGF-I or AE: Is addressed by the treatment condition of interest attribute
- There are no remaining intercurrent events
- Population-level summary: Event rate per 100 patient years

Rationale for estimand: The primary estimand assesses the expected safety profile in relation to incidence of AEs for a future population (SGA, TS, NS or ISS) while on somapacitan treatment for 26 weeks, if no treatment discontinuation occurs for any reason.

## Secondary estimands

The supportive secondary safety estimand regarding the incidence of AEs possibly or probably related to somapacitan from baseline up to week 26 of somapacitan treatment will be evaluated in a similar way as the primary endpoint including possibly or probably related to somapacitan in the endpoint attribute.

The supportive secondary safety estimand regarding the incidence of AEs from baseline to week 156 of somapacitan treatment will be evaluated in a similar way as the primary endpoint substituting 156 weeks for 26 weeks.

The supportive secondary efficacy estimands will be specified in Section [4.3.2](#).

## 1.2 Study Design

This is an interventional, multi-national, multi-centre, open-labelled, uncontrolled phase 3 study with a basket design. The study is designed to evaluate safety and efficacy of once-weekly dosing of somapacitan 0.24 mg/kg/week during 26 weeks (main phase) in children with short stature in each of the indications SGA, TS, NS and ISS. The 26-week main phase will be followed by a 130-week extension phase with once-weekly dosing of somapacitan 0.24 mg/kg/week to evaluate long-term safety. Study participants will include children with SGA, TS (only females), NS and ISS.

[figure not shown]
Approximately 60 participants in total are planned to be screened and up to 50 participants in total are planned to be enrolled (planned treated) in this study. In total, at least 40 participants are planned to complete the study. All participants will receive somapacitan 0.24 mg/kg/week.

The total treatment duration for each participant is scheduled to be 3 years. The treatment period is followed by a safety follow-up period of 30 days.

The study consists of:

- an up to 3-week screening period for participants in the indications SGA and ISS
- an up to 6-week screening period for participants in the indications TS and NS
- a 26-week interventional main phase
- a 130-week interventional extension phase
- a 30-day follow-up period

### Figure 1 Study design

## **2 Statistical Hypothesis**

No hypotheses are planned to be tested in the study.

### **2.1 Multiplicity Adjustment**

Not applicable.

### 3 Analysis Sets

The following participant analysis sets are defined within each sub-study:

| Participant analysis set (PAS) | Description   |
|--------------------------------|---|
| Full analysis set (FAS)        | All participants assigned to study intervention.        |
| Safety analysis set (SAS)      | All participants who are exposed to study intervention. |

The full analysis set will be used to analyse endpoints related to the efficacy objectives and the safety analysis set will be used to analyse the endpoints and assessments related to safety.

For the efficacy analyses, participants will be included in the analyses according to the planned investigational intervention; whereas for safety analyses, participants will be included in the analyses according to the investigational intervention they actually received.

The following data points sets are defined:

| Defined data points set (DPS) | Description  |
|-------------------------------|--|
| In-study                      | All observations from assignment to study intervention date up until visit 7 or last study contact, whichever comes first.                             |
| On-treatment                  | All observed data from first study intervention and up until visit 7, last study contact, or 14 days after last administration, whichever comes first. |

The on-treatment data point sets represent data collected in the period in which a participant is considered exposed to IMP.

FAS and In-study are used to estimate the supportive secondary efficacy estimands for Height velocity, Change in Height SDS and Change in Height Velocity SDS.

FAS and On-treatment are used to present the supportive secondary efficacy estimands for Change in IGF-I SDS and Change in IGFBP-3 SDS.

Safety analysis set and On-treatment are used to present the primary estimand for the primary objective and all other safety data.

## 4 Statistical Analyses

### 4.1 General Considerations

Descriptive statistics will be performed as described in the sections [4.2](#) and [4.3](#).

### 4.2 Primary Endpoint/Estimand Analysis

The primary endpoint number of adverse events will be used to support the primary objective of evaluating safety of once-weekly somapacitan during 26 weeks of treatment in children with SGA, TS, NS or ISS based on the primary estimand corresponding to the on-treatment data points set.

To support the primary estimand descriptive statistics (Number and percentage of participants who experienced adverse events, the number of events) will be derived in addition to the event rate per 100 patient years of exposure. The primary endpoint will be summarised for each indication, SGA, TS, NS or ISS. All adverse events with onset after the first administration of trial product and up until end of treatment or 14 days after last trial product administration, whichever comes first, will be included in the analysis. The adverse events will be summarised by MedDRA (Medical Dictionary for Regulatory Activities) system organ class and MedDRA preferred term. Adverse events with onset 14 days or more after last trial product administration will be reported in a separate listing.

#### 4.2.1 Definition of Endpoint

Number of adverse events (AEs) from baseline (week 0) to week 26.

#### 4.2.2 Main Analytical Approach

Safety analysis set and On-treatment are used to present the primary estimand for the primary objective.

#### 4.2.3 Sensitivity Analysis

Not applicable.

#### 4.2.4 Supplementary Analysis

Not applicable.

### 4.3 Secondary Endpoints/Estimands Analysis

#### 4.3.1 Confirmatory Secondary Endpoints

Not applicable.

#### 4.3.2 Supportive Secondary Endpoints/Estimands

##### 4.3.2.1 Supportive secondary safety endpoints/estimands

The supportive secondary safety estimand regarding the incidence of AEs possibly or probably related to somapacitan from baseline up to week 26 of somapacitan treatment will be evaluated in a similar way as the primary endpoint including AEs possibly or probably related to somapacitan in the endpoint attribute.

The supportive secondary safety estimand regarding the incidence of AEs from baseline up to week

156 of somapacitan treatment will be evaluated in a similar way as the primary endpoint substituting 156 weeks for 26 weeks.

#### 4.3.2.2 Supportive secondary efficacy endpoints/estimands

**Table 1 Supportive secondary efficacy endpoints**

| Title  | Time frame                                  | Unit               |
|--|---|--------------------|
| Height velocity  | From baseline (week 0) to visit 7 (week 26) | cm/year            |
| Change in Height SDS   | From baseline (week 0) to visit 7 (week 26) | Score a |
| Change in Height Velocity SDS  | From baseline (week 0) to visit 7 (week 26) | Score a |
| Change in IGF-I SDS  | From baseline (week 0) to visit 7 (week 26) | Score a |
| Change in IGFBP-3 SDS  | From baseline (week 0) to visit 7 (week 26) | Score a |
| Weekly average somapacitan concentration (C avg ) based on population PK analysis | From baseline (week 0) to visit 7 (week 26) | ng/ml              |

aPositive score indicates that the value is closer to or above the reference population compared to baseline.

#### Height velocity, Change in Height SDS and Change in Height Velocity SDS

The clinical question of interest for the supportive secondary efficacy endpoints Height velocity, Change in Height SDS and Change in Height Velocity SDS are: What is the mean Height velocity, Change in Height SDS or Change in Height Velocity SDS after 26 weeks of somapacitan treatment for each group of previously treated (yes/no) in the four populations (SGA, TS, NS or ISS) regardless of dose reduction due to IGF-I or AE, regardless of treatment discontinuation for any reason and regardless of initiation of ancillary therapy or medication with a special focus?

The supportive secondary estimands are defined for each of the four populations (SGA, TS, NS or ISS) with five attributes:

- The treatment condition of interest is defined as somapacitan treatment with or without ancillary therapy or medication with a special focus (treatment policy strategy).
- The population targeted by the clinical question: The treatment effect will be assessed separately for each group of previously treated (yes/no) in the four populations (SGA, TS, NS or ISS).
- Endpoints:
- Height velocity from baseline (week 0) to visit 7 (week 26)
- Change in Height SDS from baseline (week 0) to visit 7 (week 26)
- Change in Height Velocity SDS from baseline (week 0) to visit 7 (week 26)

Remaining intercurrent events: The 4 intercurrent events ‘dose reduction due to IGF-I or AE’, ‘treatment discontinuation for any reason’, ‘initiation of ancillary therapy’ and ‘medication with a special focus’, are all addressed by the treatment condition of interest attribute. There are no remaining intercurrent events.

- Population-level summary: Mean change

Rationale for estimands: The estimands assess the expected benefit a future population (SGA, TS, NS or ISS) can achieve if prescribed somapacitan. By not placing any restrictions on treatment adherence, these estimands aim to obtain a difference as close as possible to the one that can be expected in clinical practice, provided that the dose reduction, treatment adherence and use of ancillary therapy in the study reflects what would be seen in clinical practice.

The supportive secondary estimands will be evaluated based on all participants where both baseline and week 26 data are collected. To support the supportive secondary estimands SD, median, min and max values will also be derived for the supportive secondary endpoints.

### Change in IGF-I SDS and Change in IGFBP-3 SDS

The clinical question of interest for the supportive secondary efficacy endpoints Change in IGF-I SDS and Change in IGFBP-3 SDS from baseline (week 0) to visit 7 (week 26) are: What is the mean change after 26 weeks of somapacitan treatment within each group of previously treated (yes/no) in the four populations (SGA, TS, NS or ISS) patients while on treatment regardless of dose reduction due to IGF-I or AE or medication with a special focus?

The supportive secondary estimands are defined for each of the four populations (SGA, TS, NS or ISS) with five attributes:

- The treatment condition of interest is defined as somapacitan regardless of dose reduction or medication with a special focus.
- The population targeted by the clinical question: The treatment effect will be assessed separately for each group of previously treated (yes/no) in the four populations (SGA, TS, NS or ISS)
- Endpoints:
  - Change in IGF-I SDS from baseline week 0 to week 26
  - Change in IGFBP-3 SDS from baseline week 0 to week 26
- Remaining intercurrent events:
  - Treatment discontinuation for any reason: Participant's data will be included up to 14 days after treatment discontinuation. Data collected 14 days after the intercurrent event will be regarded as not relevant for the estimation of the treatment effect.
  - Initiation of medication with a special focus: Addressed by the treatment condition of interest attribute.
  - Dose reduction due to IGF-I or AE: Addressed by the treatment condition of interest attribute. There are no remaining intercurrent events.
- Population-level summary: Mean change

Rationale for estimand: The supportive secondary estimand assesses the expected benefit a future population (SGA, TS, NS or ISS) can achieve if prescribed somapacitan if no treatment discontinuation had occurred.

The supportive secondary estimands will be evaluated based on all participants where both baseline and week 26 data are collected. To support the supportive secondary estimands SD, median, min and max values will also be derived for the supportive secondary endpoints.

FAS and In-study are used to estimate the supportive secondary efficacy estimands for Height velocity, Change in Height SDS and Change in Height Velocity SDS.

FAS and On-treatment are used to present the supportive secondary efficacy estimands for Change in IGF-I SDS and Change in IGFBP-3 SDS.

### Pharmacokinetic and/or pharmacodynamic modelling

Pharmacokinetic (PK) and pharmacodynamic (PD) modelling based on the somapacitan concentration and IGF-I data from the study will be performed.

The objective of the PK/PD modelling analysis is to characterise the weekly PK/PD profile, weekly average exposure ( $C_{avg}$ ) and weekly IGF-I average levels following somapacitan treatment in SGA, TS, NS and ISS.

A more technical and detailed elaboration of the PK/PD modelling will be given in a modelling analysis plan (MAP), which will be prepared prior to database lock. Weekly average exposure ( $C_{avg}$ ) based on population PK/PD modelling will be reported as a secondary endpoint. Other PK/PD modelling results will be reported in a separate modelling report, which will not be part of the CSR. The individual somapacitan concentration data will be tabulated in the bioanalytical report.

#### **4.4 Exploratory Endpoints Analysis**

Not applicable.

#### **4.5 Other Safety Analysis**

##### **Safety laboratory assessments**

Safety laboratory assessments (biochemistry, haematology, glucose metabolism, coagulation parameters (NS), and lipids) will be summarised by time of assessment for each indication, SGA, TS, NS or ISS. All abnormal values will be listed.

##### **Vital signs**

Vital signs (electrocardiogram, transthoracic electrocardiogram (TS, NS)) will be summarised by time of assessment for each indication, SGA, TS, NS or ISS. The investigator's evaluation of vital signs will be tabulated by time of assessment for each indication, SGA, TS, NS or ISS.

##### **Antibodies**

For confirmed anti-somapacitan antibody positive samples, the anti-somapacitan positive crossreactivity to hGH antibodies and in vitro neutralising effect will be tabulated by time of assessment for each indication, SGA, TS, NS or ISS.

##### **4.5.1 Extent of Exposure**

Not applicable.

##### **4.5.2 Adverse Events**

Adverse events will be displayed as per the primary and secondary endpoints.

##### **4.5.3 Additional Safety Assessments**

Not applicable.

#### **4.6 Other Analysis**

##### **4.6.1 Other parameters**

**Table 2 Overview of other parameters**

| Title  | Time frame  | Unit                 |
|--|---|----------------------|
| Child treatment burden measure: GH-INJ-CTB-Physical e                 | Visit 5   | Score a   |
| Child treatment burden measure: GH-INJ-CTB-Emotional Well-being e     | Visit 5   | Score a   |
| Child treatment burden measure: GH-INJ-CTB-Interference e             | Visit 5   | Score a   |
| Child treatment burden measure: GH-INJ-CTB-Overall treatment burden e | Visit 5   | Score a   |
| Patient Preference: GH-PPQ-Child e                                    | Visit 5   | Categorical response |
| Near adult height (NAH)  | 18 months prior to screening to visit 18 (week 156) | Yes/No               |
| Change in height SDS at the visit when NAH is reached                            | From baseline (week 0) to the visit NAH is reached  | Score b   |
| Midparental target height (MPH)  | Screening (visit 1)                                 | cm                   |
| MPH SDS  | Screening (visit 1)                                 | Score c   |
| Index of genetic height potential  | From baseline (week 0) to the visit NAH is reached  | Score d   |
| Change in interventricular Septum end diastole (IVSed) SDS                       | From baseline (week 0) to visit 7 (week 26)         | Score b   |
| Change in left ventricle posterior wall end diastole (LVPWed) SDS                | From baseline (week 0) to visit 7 (week 26)         | Score b   |
| Change in left ventricle inner dimension end diastole (LVIDed) SDS               | From baseline (week 0) to visit 7 (week 26)         | Score b   |
| Change in left ventricle inner dimension end systole (LVIDes) SDS                | From baseline (week 0) to visit 7 (week 26)         | Score b   |
| Change in sitting height/height (SH/H)   | From baseline (week 0) to visit 7 (week 26)         | Ratio                |
| Change in sitting height/height SDS (SH/H SDS)                                   | From baseline (week 0) to visit 7 (week 26)         | Ratio                |
| Change in bone age/chronological age   | From screening (visit 1) to visit 9 (week 52)       | Ratio                |

aNegative score indicates that treatment burden is less compared to baseline.bPositive score indicates that the value is closer to or above the reference population compared to baseline.cNegative values indicate that the values are lower than the reference population.dNegative values indicate that the NAH is below the genetic height potential.eOnly to be collected from participants switching to somapacitan from daily GH treatment.

Height Velocity at visit 9 (week 52), Change in Height SDS from baseline (week 0) to visit 9 (week 52), Change in Height Velocity SDS from baseline (week 0) to visit 9 (week 52), Change in IGF-1 SDS from baseline (week 0) to visit 9 (week 52) and Change in IGFBP-3 SDS from baseline (week 0) to visit 9 (week 52) will be derived as parameters in the same way as the corresponding secondary endpoints at visit 7 (week 26).

The parameters will be summarised for relevant indications, SGA, TS, NS or ISS.

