Section 8.3.1 Time period and frequency for collecting AE information	Text has been updated regarding collection of medication errors and injection sites.	To accommodate changes due to addition of extension period II
Section 8.6 Genetics	Text added to specify the need to include special laboratory results in the eCRF	Clarification
Section 9.3.6 Other analyses	The evaluation of near adult height (NAH) was extended up to end of treatment (extension period II).	To ensure NAH data is evaluated until end of treatment.
Section 10.2 Appendix 2: Clinical laboratory tests Table 10-3 Other protocol-required laboratory assessments	The text 'NS' added to specify that if genetic testing for NS is not accessible at the local laboratory, the analysis can be conducted by a designated special laboratory.	Clarification
Section 10.2 Appendix 2: Clinical laboratory tests Table 10-4 Timing of visits and blood sampling	Updated to include visits during extension period II.	To accommodate changes due to addition of extension period II
Section 10.8 Dosing Tables	Dose reduction tables were added for somapacitan	Clarification
10.10.2 Visits	The text '(Visit 17)' has been deleted.	To align with the changes made to the study due to addition of extension period II.
Section 10.13 Appendix 13: Protocol amendment history	Text under Protocol version 4.0 'Exclusion criteria 10' has been changed to 'Exclusion criteria 8'.	Correction
Throughout the Protocol	The term "phase" has been replaced with "period" when referring the main, extension I, and extension II periods.	To ensure consistency through the protocol

Table of Contents

	Page
Protocol amendment and summary of changes table	2
Table of Contents	5
1 Protocol summary	9
1.1 Synopsis	9
1.2 Flowchart for main and extension period I	15
1.3 Flowchart for extension period II	24
2 Introduction	30
2.1 Study rationale	30
2.2 Background	31
2.2.1 Short stature	31
2.2.2 Treatment of short stature	31
2.2.3 Included populations	31
2.2.3.1 Small for Gestational Age: Children born small for gestational age with insufficient catch-up growth by 2 years of age or older	32
2.2.3.2 Turner Syndrome	32
2.2.3.3 Noonan Syndrome	32
2.2.3.4 Idiopathic Short Stature	33
2.2.4 Study Intervention	33
2.2.4.1 Somapacitan	33
2.2.4.2 Somapacitan nonclinical data	33
2.2.4.3 Somapacitan clinical data	33
2.3 Benefit-risk assessment	34
2.3.1 Risk assessment	34
2.3.2 Benefit assessment	38
2.3.3 Overall benefit-risk conclusion	38
3 Objectives, endpoints and estimands	39

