4.1 Overall design

This is an interventional, multi-national, multi-centre, open-labelled, uncontrolled phase 3 study with a basket design. The study is designed to evaluate safety and efficacy of once-weekly dosing of somapacitan 0.24 mg/kg/week during 26 weeks (main period) in children with short stature in each of the indications SGA, TS, NS and ISS. The 26-week main period will be followed by a 130-week extension period I with once-weekly dosing of somapacitan 0.24 mg/kg/week to evaluate long-term safety. Further, participants, who complete the extension period I when somapacitan is not available to be prescribed for children with SGA, TS, NS or ISS in their country, can continue treatment in extension period II which will last until somapacitan becomes available for prescription in their country or October 2027 (at the latest). Participants will receive somapacitan at 0.24 mg/kg/week. Study participants will include children with SGA, TS (only females), NS and ISS.

Children above or equal to 10.0 years (female participants with SGA, TS, NS, and ISS) or 11.0 years (male participants with SGA, NS, and ISS) and below 18.0 years are not included in the pivotal study NN8640-4467. Based on a recommendation from the Health Authorities, this age group will be investigated in this study NN8640-4469.

[figure not shown]
Approximately 60 participants in total are planned to be screened and up to 50 participants in total are planned to be enrolled (planned treated) in this study. In total, at least 40 participants are planned to complete the study. All participants will receive somapacitan 0.24 mg/kg/week.

The total treatment duration for participants in the study, up to the end of the extension period I, is scheduled to be 3 years. For participants who remain on treatment in the extension period II, the total study duration will be up to 5 years. The treatment period is followed by a safety follow-up period of 30 days.

The study consists of:

- an up to 3-week screening period for participants in the indications SGA and ISS
- an up to 6-week screening period for participants in the indications TS and NS
- a 26-week interventional main period
- a 130-week interventional extension period I
- up to 91-week interventional extension period II
- a 30-day follow-up period

Figure 4-1 Study design

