9.3.6 Other analyses

Other parameters

Table 9-2 Overview of other parameters

Title	Time frame	Unit	Details
Child treatment burden measure: GH-INJ-CTB-Physical ^e	Visit 5	Score ^a	GH-INJ-CTB-Physical score at week 13 (visit 5). GH-INJ-CTB – Physical score is derived as the sum of the 4 items (0=Not at all, 1=A little, 2=Some, 3=A lot, 4=Extreme) normalised to a 0-100-point scale as: Physical (question 1-4): (Sum/16)*100
Child treatment burden measure: GH-INJ-CTB-Emotional Well-being ^e	Visit 5	Score ^a	GH-INJ-CTB-Emotional Well-being score at week 13 (visit 5). GH-INJ-CTB – Emotional Well-being score is derived as the sum of the 4 items (0=Not at all, 1=A little, 2=Some, 3=A lot, 4=Extreme) normalised to a 0-100-point scale as: Emotional Well-being (question 5-10): (Sum/24)*100
Child treatment burden measure: GH-INJ-CTB-Interference ^e	Visit 5	Score ^a	GH-INJ-CTB-Interference score at week 13 (visit 5). GH-INJ-CTB – Interference score is derived as the sum of the 4 items (0=Not at all, 1=A little, 2=Some, 3=A lot, 4=Extreme) normalised to a 0-100-point scale as: Interference: (question 11-14): (Sum/16)*100
Child treatment burden measure:	Visit 5	Score ^a	GH-INJ-CTB-Overall treatment burden score at week 13 (visit 5).

Title	Time frame	Unit	Details
GH-INJ-CTB Overall treatment burden ^e			GH-INJ-CTB – Overall treatment burden score is derived as the mean of the GH-INJ-CTB – Physical score, GH-INJ-CTB - Emotional Well-being score and GH-INJ-CTB – Interference score.
Patient Preference: GH-PPQ-Child ^e	Visit 5	Categorical response	Patient Preference GH-PPQ-Child at week 13 (visit 5) (Previous treatment, Current treatment, No preference).
Near adult height (NAH)	18 months prior to screening to end of treatment	Yes/No	Near adult height (NAH) will be derived. NAH is defined as HV < 2 cm/year calculated over a period of at least 9 months, males have reached a bone age of ≥ 16 years and females has reached a bone age of ≥ 14 years. If bone age is not available, then males have reached a chronological age of ≥ 17 years and females have reached a chronological age of ≥ 15 years. Historical height measurements collected at screening will be included in the derivation.
Change in height SDS at the visit when NAH is reached	From baseline (week 0) to the visit NAH is reached	Score ^b	Derived as the Height SDS value at baseline week 0 subtracted from the Height SDS value at the visit where NAH is reached.

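### SAP 1.0 ends the near-adult-height flag at week 156, under a visit label that does not fit the flowchart, while the current protocol runs it to end of treatment

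*SAP*

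**What the plan says.** **SAP.** The table of other parameters in section 4.6.1 lists NAH as a Yes/No variable with the time frame "18 months prior to screening to visit 18 (week 156"). The derivation table in Appendix 1 (section 6.1) repeats it. The Version History states that the SAP "is based on the protocol version 3.0 dated 21 December 2022". Section 1.2 says "The total treatment duration for each participant is scheduled to be 3 years" and does not mention extension period II. Section 4.8 declares no departure from the protocol-planned analysis.

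**Current protocol.** Table 9-2 in section 9.3.6 gives the NAH time frame as "18 months prior to screening to end of treatment". The summary of changes confirms that this was deliberate: "The evaluation of near adult height (NAH) was extended up to end of treatment (extension period II"). That log is cited only for intent; the conflict lies between the SAP and the current Table 9-2.

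**NAH-dependent parameters.** In both documents, change in height SDS at NAH and the index of genetic height potential run from baseline to whichever visit NAH is reached at. Neither has a week-156 limit.

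**The concern.** A time frame tells the programmer which height and bone-age records may turn the flag to Yes. The SAP and the current protocol now give different answers for any child treated beyond week 156. The SAP also ties its cut-off to a visit that the flowchart places at another time and that those children do not attend.

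At stake is the NAH tabulation and its agreement with two other outputs: the discontinuation reasons and the two parameters computed at the NAH visit. With ten planned completers per indication, one child classed differently moves that indication's NAH proportion by 1/10, or 10 percentage points.

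**Working it through.** **Inputs.** Period lengths from Protocol 4.1: "a 26-week interventional main period", "a 130-week interventional extension period I" and "up to 91-week interventional extension period II". Visit timing from the flowcharts: visit 17 at week 156 + 5 days and visit 18 at week 156 + 30 days (Protocol 1.2); visits 19 to 25 at weeks 169, 182, 195, 208 + 2 days, 221, 234 and 247 (Protocol 1.3).

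**1. The SAP's week number.** 26 + 130 = 156. Week 156 reproduces as the end of extension period I.

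**2. The SAP's visit number.** Visit 17 = 156 + 5/7 = 156.7 weeks. Visit 18 = 156 + 30/7 = 160.3 weeks. The label does not reproduce: week 156 belongs to visit 17. The flowchart footnotes make visit 17 the end-of-treatment visit for those who stop there, and limit visit 18 to participants who end the trial after extension period I or discontinue before visit 17. A child in extension period II has visit 99 as follow-up instead. (Protocol 4.4 still counts visit 18 towards study completion for all participants, but the footnote is explicit.)

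**3. Length of the omitted stretch.** Maximum treatment = 26 + 130 + 91 = 247 weeks.
- In years: 247 × 7/365.25 = 4.73, against 156 × 7/365.25 = 2.99.
- Outside the SAP window: 247 − 156 = 91 weeks at most, or 91/247 = 36.8% of one participant's longest possible treatment.

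**4. Why extension period II events are new.** Protocol 7.1 lists reaching NAH among the reasons for which study treatment must be stopped. If that is followed, a child who passes into extension period II has not met NAH by visit 17, so any NAH there falls after the SAP cut-off.

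The look-back works the same way. Height velocity must be calculated over at least 9 months, which is 9 × 30.4375/7 = 39.1 weeks, and 156 − 39.1 = 116.9. A qualifying interval that starts after about week 117 cannot be completed by week 156.

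**5. Are the data there?** Yes. Protocol 1.3 schedules height at visits 19 to 25 and at visit 98. Bone-age X-ray is at visit 22 and at visit 98, unless one was done in the previous 6 months.

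**6. Consistency inside the SAP.** The flag is capped and the two parameters that use it are not. Take a child who first meets the definition at week 208. One programmer sets NAH = No and leaves both parameters missing. Another follows the parameters' own time frame and reports a change in height SDS at NAH for a child flagged No. The SAP does not say which is intended.

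**The case against.** The best defence is that this is version lag, openly declared. The SAP names protocol 3.0 as its basis and describes a 3-year study, and a week-156 window suits that scope. Read against that version, the statement in section 4.8 may be correct, and the visit label cannot be checked because the version 3.0 flowchart is not supplied. The current protocol already states the fuller window, so harm arises only if extension period II data are reported under SAP 1.0 unrevised. All of this stands. It limits the weight of the point but does not remove it, because SAP 1.0 is the plan supplied alongside the current protocol.

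It is also fair to say that NAH reached in extension period II would not vanish from the database: Protocol 7.1 requires the primary reason for discontinuation in the CRF. And the SAP has no explicit rule coding later events as No; that follows from reading a Yes/No variable with a closed window literally. Both are correct, and together they produce the contradiction described: a recorded discontinuation for NAH beside a derived No.

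Some stronger readings are tempting but unsupported:

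- **That about 37% of the data or of NAH events are lost.** The figure is one participant's maximum. Extension period II is open only where the product is not yet available for prescription, and has no fixed length (Protocol 4.4). The documents give no number entering it or reaching NAH there.
- **That the youngest entrants are the ones dropped.** Suppose bone age tracks chronological age. A boy entering at 11.0 years is 11.0 + 4.73 = 15.73 at week 247, still short of the bone-age limit of 16, so neither window would capture him. Bone-age delay, allowed up to 2 years in treatment-naïve ISS, pushes this later.
- **That visit 18 has no height measurement.** The flowchart's height row is broken in the available text and does not settle it.
- **That the two dependent parameters are themselves cut at week 156.** They are not; the problem is inconsistency with the flag.

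**Conclusion.** The point holds as a correction to the SAP. The two current documents give different NAH windows, the SAP states its own in two places, and its visit label does not match the current flowchart. If NAH is applied as a stopping reason as Protocol 7.1 requires, the SAP window, read literally, misses every NAH event in extension period II.

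The size is up to 91 weeks per participant, in an unknown number of participants. NAH and its two companions are descriptive other parameters. The primary and secondary endpoints are untouched, and no hypothesis is tested. This is a minor point, worth fixing because the fix is simple and the present text allows contradictory tables. The conclusion assumes that SAP 1.0 would be used unrevised when extension period II is reported.

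**What to change.** In SAP section 4.6.1 and Appendix 1, change the NAH time frame to run from 18 months before screening to end of treatment, defined as visit 17 or 17A, or visit 98 for participants in extension period II. State that change in height SDS at NAH and the index of genetic height potential are derived over that same window, so that a value exists only when the flag is Yes.

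Update the protocol version cited in the Version History and Introduction, add extension period II to section 1.2, and revise section 4.8 to match: either the SAP now agrees with the current protocol, or any departure kept on purpose is listed there.

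The cost is one SAP version update, made before extension period II data are analysed. It needs no new data and no change to study conduct.
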